8.0 Dosage Modification Based on Adverse Events

If multiple adverse events are seen, administer dose based on greatest reduction required for any single adverse event observed. Reductions or increases apply to treatment given in the preceding cycle and are based on adverse events observed since the prior dose.

ALERT: *ADR reporting may be required for some adverse events (See Section 10)*

8.1 Dose Levels (Based on Adverse Events in Tables 8.2)

Dose Level	Ponatinib
0*	45mg PO once daily
-1	30mg PO once daily
-2	15mg PO once daily

*Dose level 0 refers to the starting dose.

8.2

→ → *Use the NCI Common Terminology Criteria for Adverse Events (CTCAE) version 4.0* unless otherwise specified* ← ←

CTCAE System/Organ/Class (SOC)	ADVERSE EVENT	AGENT	ACTION**
BASED ON INTERVAL ADVERSE EVENT			
Investigations	Neutrophil count decreased ≥ Grade 3	Ponatinib	Omit ponatinib Resume at 45 mg after recovery to ≤ grade 1 Recurrence at 45 mg: Omit ponatinib Resume at 30 mg after recovery to ≤ grade 1 Recurrence at 30 mg: Omit ponatinib Resume at 15 mg after recovery to ≤ grade 1 Recurrence at 15 mg: Discontinue ponatinib

→ → Use the NCI Common Terminology Criteria for Adverse Events (CTCAE) version 4.0* unless otherwise specified ← ←			
CTCAE System/Organ/Class (SOC)	ADVERSE EVENT	AGENT	ACTION**
	Platelet count decreased \geq Grade 3		
Omit ponatinib Resume at 45 mg after recovery to \leq grade 1
 
Recurrence at 45 mg: Omit ponatinib Resume at 30 mg after recovery to \leq grade 1
 
Recurrence at 30 mg: Omit ponatinib Resume at 15 mg after recovery to \leq grade 1
 
Recurrence at 15 mg: Discontinue ponatinib

	Serum amylase increased \geq Grade 3 with no radiographic findings	Ponatinib	
Omit ponatinib Resume at 45 mg after recovery to \leq grade 1
 
Recurrence at 45 mg: Omit ponatinib Resume at 30 mg after recovery to \leq grade 1
 
Recurrence at 30 mg: Omit ponatinib Resume at 15 mg after recovery to \leq grade 1
 
Recurrence at 15 mg: Discontinue ponatinib

	Serum amylase increased \geq Grade 3 with radiographic findings or Grade 4	Ponatinib	
Omit ponatinib Repeat imaging according to clinical care After resolution by imaging, resume at 30 mg after recovery to \leq grade 1
 
Recurrence at 30 mg: Repeat above Resume at 15 mg after recovery to \leq grade 1
 
Recurrence at 15 mg: Discontinue ponatinib

→ → Use the NCI Common Terminology Criteria for Adverse Events (CTCAE) version 4.0* unless otherwise specified ← ←			
CTCAE System/Organ/Class (SOC)	ADVERSE EVENT	AGENT	ACTION**
	Alanine aminotransferase increased (ALT) and/or Aspartate aminotransferase increased (AST) ≥ Grade 3	Ponatinib	Omit ponatinib Resume at 30 mg after recovery to ≤ grade 1 Recurrence at 30 mg: Omit ponatinib Resume at 15 mg after recovery to ≤ grade 1 Recurrence at 15 mg: Discontinue ponatinib
	Alanine aminotransferase increased (ALT) OR Aspartate aminotransferase increased (AST) ≥ Grade 3 AND Blood bilirubin increased ≥ 2 x ULN AND Alkaline phosphatase > 2 x ULN	Ponatinib	Discontinue ponatinib
Gastrointestinal Disorders	Pancreatitis ≥ Grade 2	Ponatinib	Omit ponatinib Perform ultrasound or abdominal CT scan with contrast If imaging is positive, continue to omit ponatinib and repeat according to clinical care If imaging is negative, or after resolution by imaging, resume at 45 mg after recovery to ≤ grade 1 Recurrence at 45 mg: Repeat above, except resume at 30 mg after recovery to ≤ grade 1 Recurrence at 30 mg: Repeat above, except resume at 15 mg after recovery to ≤ grade 1 Recurrence at 15 mg: Discontinue ponatinib

→ → Use the NCI Common Terminology Criteria for Adverse Events (CTCAE) version 4.0* unless otherwise specified ← ←			
CTCAE System/Organ/Class (SOC)	ADVERSE EVENT	AGENT	ACTION**
	Pancreatitis ≥ Grade 3	Ponatinib	Omit ponatinib Perform ultrasound or abdominal CT scan with contrast If imaging is positive, continue to omit ponatinib and repeat according to clinical care If imaging is negative, or after resolution by imaging, resume at 30 mg after recovery to ≤ grade 1 Recurrence at 30 mg: Repeat above, except resume at 15 mg after recovery to ≤ grade 1 Recurrence at 15 mg: Discontinue ponatinib
	Pancreatitis ≥ Grade 4	Ponatinib	Discontinue ponatinib
Nervous System Disorders	Stroke any Grade	Ponatinib	Discontinue ponatinib
	Peripheral sensory neuropathy ≥ Grade 2	Ponatinib	Please see section 8.43 below for guidance
Cardiac Disorders	Left ventricular systolic dysfunction ≥ Grade 3	Ponatinib	Omit ponatinib Resume at 45 mg after recovery to ≤ grade 1 Recurrence at 45 mg : Omit ponatinib Resume at 30 mg after recovery to ≤ grade 1 Recurrence at 30 mg: Omit ponatinib Resume at 15 mg after recovery to ≤ grade 1 Recurrence at 15 mg: Discontinue ponatinib
	Left ventricular systolic dysfunction ≥ Grade 4		Discontinue ponatinib
	Myocardial Infarction any Grade		Discontinue ponatinib

→ → Use the NCI Common Terminology Criteria for Adverse Events (CTCAE) version 4.0* unless otherwise specified ← ←

CTCAE System/Organ/Class (SOC)	ADVERSE EVENT	AGENT	ACTION**
Skin and subcutaneous tissue disorders	Rash maculo-papular ≥ Grade 2 despite optimal symptomatic therapy	Ponatinib	Omit ponatinib Resume at 45 mg after recovery to ≤ grade 1 Recurrence at 45 mg: Omit ponatinib Resume at 30 mg after recovery to ≤ grade 1 Recurrence at 30 mg: Omit ponatinib Resume at 15 mg after recovery to ≤ grade 1 Recurrence at 15 mg: Discontinue ponatinib
	Rash maculo-papular ≥ Grade 3 despite optimal symptomatic therapy		Omit ponatinib Resume at 30 mg after recovery to ≤ grade 1 Recurrence at 30 mg: Omit ponatinib Resume at 15 mg after recovery to ≤ grade 1 Recurrence at 15 mg: Discontinue ponatinib
Vascular Disorders			
	Thromboembolic event ≥ Grade 1		Discontinue ponatinib

→ → Use the NCI Common Terminology Criteria for Adverse Events (CTCAE) version 4.0* unless otherwise specified ← ←			
CTCAE System/Organ/Class (SOC)	ADVERSE EVENT	AGENT	ACTION**
	Hypertension Grade 2 or 3		
Antihypertensive medication should be initiated or optimized to achieve target blood pressure before interruption or dose reduction of the study treatment at the discretion of the investigator. If hypertension is persistent despite adequate anti-HTN therapy including titration of anti-HTN medication or introduction of additional anti-HTN medications, dose interruption and reduction is recommended according to the below guidelines:
 
Hold ponatinib Resume at 30 mg after recovery to ≤ grade 1
 
Recurrence at 30 mg Omit ponatinib Resume at 15 mg after recovery to ≤ grade 1
 
Recurrence at 15 mg Discontinue ponatinib

	Hypertension ≥ Grade 4	Ponatinib	
Omit ponatinib Resume at 30 mg after recovery to ≤ grade 1
 
Recurrence at 30 mg Omit ponatinib Resume at 15 mg after recovery to ≤ grade 1
 
Recurrence at 15 mg Discontinue ponatinib

Injury, poisoning and procedural complications	Wound complication ≥ Grade 2	Ponatinib	See section 8.47 for guidance
General disorders and administrative site conditions	Edema limbs ≥ Grade 2	Ponatinib	See section 8.45 for guidance
Eye Disorders	Eye Disorders – Other	Ponatinib	See section 8.44 for guidance

→ → Use the NCI Common Terminology Criteria for Adverse Events (CTCAE) version 4.0* unless otherwise specified ← ←

CTCAE System/Organ/Class (SOC)	ADVERSE EVENT	AGENT	ACTION**
Other Non-Hematologic events	≥ Grade 3	Ponatinib	Omit drug and follow patient at least weekly until adverse event has resolved to grade ≤ 2, restart agent at next lower dose level. See sections 8.41 through 8.47 for guidance on other non-hematologic events

* Located at http://ctep.cancer.gov/protocolDevelopment/electronic_applications.ctc.htm

** Use the following to describe actions in the Action column:

- Omit = Treatment is not given for the day/days that are omitted and will not be made up, but treatment may resume once the adverse event has resolved as mandated in Table 8.2. For example, if treatment is omitted on Day 8, but the adverse event has resolved by Day 15, treatment may resume on Day 15.
- Hold/Delay = Treatment can be made up as part of this cycle
- Discontinue = Treatment is totally stopped

NOTE: If the patient experiences a significant adverse event requiring a dose reduction at the start of the next cycle, then the dose will remain lowered for that entire subsequent cycle. If that cycle is completed with no further adverse events >Grade 2, then the dose may be increased, at the investigator's discretion, one level at a time, in the following cycles.

NOTE: Adverse events requiring a dose-reduction step for any or all drugs beyond the two dose-reduction steps (levels -1 and -2) will be at the discretion of the treating physician, if the decision is made for the patient to be kept on study. These dose reductions must be clearly recorded in reported clinical data.

- 8.3 A new course of treatment may begin on the scheduled Day 1 of a new cycle if:
- The ANC is $\geq 1500/\mu\text{L}$;
 - The platelet count is $\geq 75,000/\mu\text{L}$;
 - Any other Ponatinib related adverse event that may have occurred has resolved to \leq Grade 1 or baseline severity.

If these conditions are not met on scheduled Day 1 of a new cycle, the subject will be evaluated at least weekly and the new cycle of treatment will not be initiated until the adverse event has resolved as described above.

When therapy is resumed it will be considered day one of this new cycle. If Ponatinib was halted during the previous cycle and was restarted with a one-level dose reduction without requiring an interruption for the remainder of the cycle, then that reduced dose level will be initiated on Day 1 of the new cycle. **If ponatinib was omitted for the remainder of the previous cycle or if the new cycle is delayed due to adverse event newly encountered on the scheduled Day 1**, then the scheduled cycle will be started with a one-level dose reduction. If the study drug cannot be restarted within 28 days of the

scheduled Day 1 of a given cycle, the patient will be removed from study treatment and will proceed to event monitoring.

8.4 Additional adverse event guidance:

8.41 Hepatotoxicity: Iclusig can cause hepatotoxicity, including liver failure and death. Fulminant hepatic failure leading to death occurred in an Iclusig-treated patient within one week of starting Iclusig. Two additional fatal cases of acute liver failure also occurred. The fatal cases occurred in patients with blast phase CML (BP-CML) or Philadelphia chromosome positive acute lymphoblastic leukemia (Ph+ ALL). Severe hepatotoxicity occurred in all disease cohorts. Iclusig treatment may result in elevation in ALT, AST, or both. Monitor liver function tests at baseline, then at least monthly or as clinically indicated. Interrupt, reduce, or discontinue Iclusig as clinically indicated.

8.42 Pancreatitis: Clinical pancreatitis occurred in 6% (28/449) of patients (5%, grade 3) treated with Iclusig. Pancreatitis resulted in discontinuation or treatment interruption in 6% of patients (25/449). The incidence of treatment-emergent lipase elevation was 41%. Check serum lipase every 2 weeks for the first 2 months and then monthly thereafter or as clinically indicated. Consider additional serum lipase monitoring in patients with a history of pancreatitis or alcohol abuse. Dose interruption or reduction may be required. In cases where lipase elevations are accompanied by abdominal symptoms, interrupt treatment with Iclusig and evaluate patients for pancreatitis. Do not consider restarting Iclusig until patients have complete resolution of symptoms and lipase levels are less than 1.5 x ULN.

8.43 Neuropathy: Peripheral and cranial neuropathy have occurred in Iclusig-treated patients. Overall, 13% (59/449) of Iclusig-treated patients experienced a peripheral neuropathy event of any grade (2%, grade 3/4). In clinical trials, the most common peripheral neuropathies reported were peripheral neuropathy (4%, 18/449), paresthesia (4%, 17/449), hypoesthesia (2%, 11/449), and hyperesthesia (1%, 5/449). Cranial neuropathy developed in 1% (6/449) of Iclusig-treated patients (<1%, grade 3/4). Of the patients who developed neuropathy, 31% (20/65) developed neuropathy during the first month of treatment. Monitor patients for symptoms of neuropathy, such as hypoesthesia, hyperesthesia, paresthesia, discomfort, a burning sensation, neuropathic pain, or weakness. Consider interrupting Iclusig and evaluate if neuropathy is suspected.

8.44 Ocular Toxicity: Serious ocular toxicities leading to blindness or blurred vision have occurred in Iclusig-treated patients. Retinal toxicities including macular edema, retinal vein occlusion, and retinal hemorrhage occurred in 3% of Iclusig-treated patients. Conjunctival or

corneal irritation, dry eye, or eye pain occurred in 13% of patients. Visual blurring occurred in 6% of the patients. Other ocular toxicities include cataracts, glaucoma, iritis, iridocyclitis, and ulcerative keratitis. Conduct comprehensive eye exams at baseline and periodically during treatment.

8.45 Fluid Retention: Serious fluid retention events occurred in 3% (13/449) of patients treated with Iclusig. One instance of brain edema was fatal. In total, fluid retention occurred in 23% of the patients. The most common fluid retention events were peripheral edema (16%), pleural effusion (7%), and pericardial effusion (3%). Monitor patients for fluid retention and manage patients as clinically indicated. Interrupt, reduce, or discontinue Iclusig as clinically indicated.

8.46 Cardiac Arrhythmias: Symptomatic bradyarrhythmias that led to a requirement for pacemaker implantation occurred in 1% (3/449) of Iclusig-treated patients. Advise patients to report signs and symptoms suggestive of slow heart rate (fainting, dizziness, or chest pain). Supraventricular tachyarrhythmias occurred in 5% (25/449) of Iclusig-treated patients. Atrial fibrillation was the most common supraventricular tachyarrhythmia and occurred in 20 patients. For 13 patients, the event led to hospitalization. Advise patients to report signs and symptoms of rapid heart rate (palpitations, dizziness). Interrupt Iclusig and evaluate.

8.47 Compromised Wound Healing and Gastrointestinal Perforation: Since Iclusig may compromise wound healing, interrupt Iclusig for at least 1 week prior to major surgery. Serious gastrointestinal perforation (fistula) occurred in one patient 38 days post-cholecystectomy.

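### Twelve rows of Table 8.2 fix the restart dose in milligrams regardless of the patient's current dose, and for a first event at a reduced dose this conflicts with the re-escalation NOTE and Section 8.3

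*Combined protocol and SAP*

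**What the plan says.** Section 8.1 defines three dose levels: level 0, the starting dose, is "45mg PO once daily"; level -1 is "30mg PO once daily"; level -2 is "15mg PO once daily".

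Table 8.2 then gives actions by event. Twelve rows allow a restart at a stated milligram dose when the event first occurs. In five of them the instruction begins "Omit ponatinib Resume at 45 mg after recovery to" Grade 1 or less. A sixth, pancreatitis from Grade 2, reads "If imaging is negative, or after resolution by imaging, resume at 45 mg after recovery to" that same grade. The other six restart at 30 mg. In all twelve, the further steps down, and finally discontinuation, are triggered by a recurrence at a named dose.

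Three other texts bear on the same decision:

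- Section 8.0: if several events are seen, the greatest reduction that any one of them requires applies. It adds: "Reductions or increases apply to treatment given in the preceding cycle and are based on adverse events observed since the prior dose".
- The first NOTE under Table 8.2: after a reduction at the start of a cycle, the lower dose is kept for that whole cycle. "If that cycle is completed with no further adverse events >Grade 2, then the dose may be increased", and then only at the investigator's discretion and by single levels.
- Section 8.3: if drug was left out for the remainder of a cycle, or the next cycle is delayed by an event newly found on its Day 1, that cycle starts one level lower.

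**The concern.** The twelve rows are written as if every patient is on 45 mg when a given event first appears. A patient who was reduced for one toxicity and later has a first event of a different type meets the first line of the new row, and that line takes no account of the earlier reduction. Followed literally, it can return the patient to a higher dose straight after a toxicity, while other parts of Section 8 restrict increases or call for a decrease.

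Two things are at stake. One is patient safety at the moment of restarting drug after an adverse event. The other is consistency: investigators who resolve the conflict differently will give different doses in the same situation, and the adverse event profile that Goal 2.22 sets out to estimate would then partly reflect those choices.

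**Working it through.** The plan states no figure to reproduce here. The check compares the first-occurrence restart dose in each of the twelve rows with each possible current dose (45, 30 and 15 mg, from Section 8.1).

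| Rows of Table 8.2 | Restart | Patient at 45 mg | Patient at 30 mg | Patient at 15 mg |
|---|---|---|---|---|
| Neutrophils, platelets, amylase without radiographic findings, left ventricular dysfunction (each from Grade 3); pancreatitis and rash (each from Grade 2): 6 rows | 45 mg | unchanged | higher: 45/30 = 1.5 times | higher: 45/15 = 3 times |
| Amylase with radiographic findings or Grade 4; ALT/AST, pancreatitis and rash (each from Grade 3); hypertension Grade 2-3; hypertension from Grade 4: 6 rows | 30 mg | lower | unchanged | higher: 30/15 = 2 times |

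Totals for a first event of a new type:

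- At 45 mg: 6 unchanged, 6 lower.
- At 30 mg: 6 higher, 6 unchanged, 0 lower.
- At 15 mg: 12 higher (6 by two levels, 6 by one).

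The Grade 2-3 hypertension row needs a caveat. Its introduction recommends interruption and reduction, so its own words do not fit a restart at the same or a higher dose.

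**Against the NOTE.** Nine of the twelve rows start at Grade 3 or above (12 - 3 = 9), so the triggering event itself means the cycle has not been free of events above Grade 2. Three rows start at Grade 2 (pancreatitis, rash, hypertension Grade 2-3). A Grade 2 event does not by itself break that condition, but the NOTE still asks for a completed cycle, a discretionary decision and a single-level step. A restart from 15 to 45 mg skips a level in any case.

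**Against Section 8.3.** Where drug was omitted to the end of the cycle, or the new cycle is delayed by a new event, Section 8.3 gives one level down. At 30 mg none of the twelve rows gives that; at 15 mg all twelve point upward.

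**Against Section 8.0.** The greatest-reduction sentence deals with several events seen, and the next sentence limits changes to events since the prior dose. The event behind an earlier reduction lies outside that interval on a plain reading. If the sentence is stretched to include it, the patient stays at the current dose, which is a third answer and still differs from Section 8.3.

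**How far the readings diverge.** Take a patient at 15 mg after hypertension who has a first Grade 3 neutropenia. The first line of the neutrophil row gives 45 mg. Treating any event at 15 mg as a recurrence gives discontinuation. The stretched Section 8.0 reading gives 15 mg.

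**The case against.** The strongest reply is that this is a gap and not an instruction to escalate. The ladders start from level 0 and step down; they do not address a first event at 30 or 15 mg. The NOTE restricts increases, Section 8.3 forces a decrease in some of the affected situations, and Section 8.0 can be read as keeping an earlier reduction in force. An investigator who reads Section 8 as a whole would probably not raise the dose.

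Much of that stands. The table does leave a case uncovered, and the higher dose appears only when a row is read by itself. But the NOTE and Section 8.3 do not remove the conflict; they are the other half of it. Nothing in Section 8 says which text prevails, Section 8.3 covers only two situations, and Section 8.0 is unclear on an earlier event.

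The objection also rules out several stronger claims that a reader might infer:

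- That the dose is raised after vascular events. Stroke, myocardial infarction and thromboembolic events are discontinuation rows, outside the twelve. So is ALT or AST elevation accompanied by raised bilirubin and alkaline phosphatase.
- That the 67% hypertension rate (Section 9.5) or the 41% lipase elevation rate (Section 8.42) shows how often this would happen. The first counts any treatment-emergent hypertension, whereas the Grade 2-3 row reaches a dose change only if hypertension persists despite adequate therapy. Table 8.2 has no lipase row.
- That the row for other non-hematologic events, with its "restart agent at next lower dose level", contradicts the twelve rows. It governs different events, and a different rule for them is not a contradiction.

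**Conclusion.** The point holds as an internal inconsistency that should be corrected. For a first event of a new type at a reduced dose, the literal text of the twelve rows gives a higher dose in six and an unchanged dose in six at 30 mg, and a higher dose in all twelve at 15 mg, with the Grade 2-3 hypertension row at odds with its own introduction. This conflicts with the NOTE and, in the two situations that it names, with Section 8.3.

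The conclusion assumes that a recurrence means a repeat of the same event, and that a first occurrence follows the first line of its row. The documents do not show how often a patient would reach this situation, so no effect on the adverse event rates or on time on treatment can be put in numbers. Nor do they support saying that the protocol intends escalation after toxicity. What they support is that its texts give different answers to the same question.

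**What to change.** Amend the wording of Section 8 so that the twelve rows, Section 8.0, the NOTE under Table 8.2 and Section 8.3 are reconciled and yield one unambiguous instruction for a first event of a new type occurring at a reduced dose. The amendment should also make clear whether a recurrence means a repeat of the same event. What the instruction should be is for the sponsor to decide; this review takes no position on it.

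The cost is a wording amendment only, with no added procedures, staff or patients.

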4.0 Test Schedule

Cycle = 28 days

Tests and procedures	Active Monitoring Phase						
	≤14 days prior to registration	Cycle 1 Day 1 (± 2 days) prior to treatment	Cycle 1 Days 8, 15, 22 prior to treatment	Cycle 2 and beyond Day 1 (± 2 days) prior to treatment	Q 8 weeks from Cycle 1 Day 1 (± 5 days)	Every 3 Cycles starting at end of Cycle 3 (± 5 days)	End of treatment
History and exam, wt, ECOG	X			X			X
Height, Child Pugh score	X						
Vitals ³	X	X	X	X			X
Hematology group WBC, ANC, Hgb, PLT	X	X	X	X			X
Chemistry group Sodium, potassium, chloride, bicarbonate, total protein, albumin, calcium, glucose, BUN, total bilirubin, creatinine, alkaline phosphatase, SGOT (AST), SGPT (ALT)	X	X		X			X
Amylase ^R	X	X	X	X			
Lipase ^R	X	X	X	X			
CA19-9		X		X ⁵			
EKG ^R	X					X	
Echocardiogram	X			X ¹⁰			
Tumor measurement and Imaging (CT or MRI as clinically)	X ¹				X ²		

indicated)							
Pregnancy test	X ⁴						
Patient questionnaire booklet	X ⁹			X ⁹			
Adverse event assessment	X		X	X			
Research Archival Tissue (optional)	X ⁸						
Research Tissue Biopsy (optional)				X ^{7,R}			X ⁶
Research blood samples (Optional)	X			X			X

1. Imaging studies such as CT scans, and MRIs can be performed ≤ 28 days prior to registration. Use same imaging throughout the study. Assessment by physical exam should be done ≤ 14 days prior to registration.
 2. Tumor assessment must be performed at least every 8 weeks. Tumor assessment should be performed at any time during the treatment cycle that disease progression is clinically suspected so that patient can go off treatment and receive other therapy.
 3. Includes weight, blood pressure, pulse and temperature
 4. Women of childbearing potential only. Must be done ≤ 7 days prior to registration.
 5. Only to be collected if $> \text{ULN}$ on Cycle 1 Day 1
 6. If patient has experienced disease progression and at such time a standard of care biopsy is ordered by the treating physician, waste specimen will be collected, fresh frozen and stored for future correlative studies. Perform only if archival specimen was available.
 7. Perform only if archival specimen was available.
 8. Archival FFPE and/or fresh frozen tissue collected in setting of standard of care procedures.
 9. Patient questionnaire booklet must be used; copies are not acceptable for this submission. Booklet should be completed by patient prior to review of treatment response and discussions of patient's general health since last treatment evaluation.

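### Table 8.2 gives two restart doses, 45 mg and 30 mg, for Grade 4 amylase without radiographic findings, and nothing settles a restart within the same cycle

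*Combined protocol and SAP*

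**What the plan says.** Table 8.2 splits serum amylase elevation into two rows.

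- **Row 1:** Grade 3 or higher "with no radiographic findings". Omit drug, then resume at 45 mg after recovery to Grade 1 or lower. Recurrences step down to 30 mg, then 15 mg, then discontinuation.
- **Row 2:** Grade 3 or higher "with radiographic findings or Grade 4". Omit drug and repeat imaging. The restart instruction begins "After resolution by imaging, resume at 30 mg", again with recovery to Grade 1 or lower. Recurrences step down to 15 mg, then discontinuation.

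The definition of Omit beneath the table allows a restart within the cycle and refers back to Table 8.2 for the conditions. Its example reads: "if treatment is omitted on Day 8, but the adverse event has resolved by Day 15, treatment may resume on Day 15".

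Section 8.3 governs new cycles. If drug was omitted for the rest of the previous cycle, or an event newly found on a scheduled Day 1 delays the new one, "then the scheduled cycle will be started with a one-level dose reduction". If drug was restarted one level lower during the previous cycle, "then that reduced dose level will be initiated on Day 1 of the new cycle".

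In Section 4.0, amylase is tested at screening, on Cycle 1 Day 1, at "Cycle 1 Days 8, 15, 22 prior to treatment", and then on Day 1 of each later cycle.

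**The concern.** Row 1 has no upper grade limit, and in row 2 the Grade 4 criterion does not depend on the imaging result. A patient with Grade 4 amylase and clean imaging therefore meets both triggers, and the rows give different restart doses. A site that applies row 1 literally can return that patient to full dose, although the next row names Grade 4 and calls for 30 mg.

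Row 2's action adds to the doubt. It ties restart to resolution on imaging, which has no clear meaning when imaging showed nothing. Row 1's action fits such a patient more naturally, so a site could be drawn to the higher dose.

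The stake is dosing safety at first restart. The statistical design is not involved.

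**Working it through.** **Step 1. The four combinations against the two triggers (first occurrence at 45 mg)**

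| Amylase grade | Imaging findings | Rows met | Restart dose |
|---|---|---|---|
| 3 | No | 1 | 45 mg |
| 3 | Yes | 2 | 30 mg |
| 4 | Yes | 2 | 30 mg |
| 4 | No | 1 and 2 | 45 mg or 30 mg |

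The overlap remains however the Grade 4 phrase in row 2 is parsed, whether as an alternative to the whole criterion or only to the imaging condition.

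**Step 2. Does other text choose a row?**

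- Section 8.0 has a greatest-reduction rule, but it is conditioned on several adverse events. Here one event meets two rows.
- Section 8.3 yields 30 mg when drug was omitted to the end of the cycle, or when an event newly found on Day 1 delays the new cycle. From Cycle 2 on, amylase is scheduled on Day 1 only, so scheduled detections there are largely settled.
- The residual row for other non-hematologic events restarts one level lower, but it covers events not listed in the table, and amylase is listed.
- The definition of Omit sends a same-cycle restart back to Table 8.2, that is, to the two conflicting rows.

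The open case is therefore an event found mid-cycle (mainly Cycle 1 Days 8, 15 and 22, or an unscheduled test) that recovers to Grade 1 or lower before that cycle ends.

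**Step 3. Size of the difference**

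Daily gap: 45 − 30 = 15 mg.

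The protocol's example, restart on Day 15 of a 28-day cycle:

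- Days remaining (Days 15 to 28): 14.
- Dose at 45 mg: 45 × 14 = 630 mg. Dose at 30 mg: 30 × 14 = 420 mg. Gap: 210 mg.
- Next cycle, with 30 mg carried over under Section 8.3: 28 × 15 = 420 mg.
- Total to the end of that cycle: 14 + 28 = 42 days; 45 × 42 = 1890 mg against 30 × 42 = 1260 mg. Gap: 630 mg.

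After a reduced cycle with no further event above Grade 2, the note under the table lets the investigator raise the dose "one level at a time, in the following cycles", so the gap need not persist.

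Ceilings on the gap within the cycle, by scheduled detection day, assuming restart the very next day:

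| Detected | Days left | Gap |
|---|---|---|
| Day 8 | 28 − 8 = 20 | 20 × 15 = 300 mg |
| Day 15 | 28 − 15 = 13 | 13 × 15 = 195 mg |
| Day 22 | 28 − 22 = 6 | 6 × 15 = 90 mg |

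**The case against.** The strongest reply is that overlapping, open-ended triggers are how this table is built. Pancreatitis, left ventricular dysfunction and rash all stack rows in this way, and a sensible reader uses the most severe row met. Moreover, Grade 4 with findings already falls under row 2's first criterion, so the Grade 4 phrase can only serve to move Grade 4 without findings into the 30 mg row. The greatest-reduction principle in Section 8.0 points the same way.

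This establishes the intent, which is 30 mg. It does not remove the conflict.

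- The other stacked rows have rising grade thresholds, so a highest-row reading works. Both amylase rows start at Grade 3 and divide on imaging, and row 1's imaging condition describes the disputed patient exactly.
- The redundancy argument cuts both ways: the open upper end of row 1 also does nothing except bring in Grade 4 without findings.
- The table can cap a grade range. The hypertension rows separate Grades 2 and 3 from Grade 4.

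On imaging, one can argue that negative imaging leaves nothing to resolve, so the condition is met by default. That reading is reasonable, but the pancreatitis Grade 3 row states the negative-imaging case expressly and row 2 does not.

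Two points on size stand. The next-day ceilings need Grade 4 to fall to Grade 1 or lower within a day, which nothing in the documents supports; they are bounds only. The 630 mg figure assumes uninterrupted dosing on both sides, and row 1 itself drops to 30 mg on recurrence. The open case is also narrow and may never arise in this trial.

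**Conclusion.** The concern holds: the two amylase rows are wrong as written for a first Grade 4 elevation without radiographic findings, and no text expressly selects a dose when drug restarts within the same cycle. The evident intent is 30 mg; the literal alternative is 45 mg.

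The difference is one dose level at first restart. The cumulative figures, 210 mg over 14 days and 630 mg over 42 days, rest on the protocol's own Day 8 to Day 15 example, on uninterrupted dosing and, for the second, on 30 mg being carried through the next cycle. The number of patients affected cannot be derived because no Grade 4 amylase rate is given; accrual is at most 30. Severity is minor. The primary endpoint, power and two-stage decision rule do not change.

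**What to change.** Edit two rows of Table 8.2.

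1. In row 1, replace the open-ended threshold with Grade 3 only, keeping the no-findings condition. Grade 4 then falls in row 2 alone.
2. In row 2, let drug resume at 30 mg after recovery to Grade 1 or lower either when imaging is negative or once findings have resolved, as the pancreatitis Grade 3 row already provides.

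A general sentence saying that the most restrictive row met governs would also resolve the dose and would cover the table's other overlaps, but row 2 would still need its negative-imaging clause.

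The cost is wording in the next amendment, with no new tests, visits or patients.
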